Dietary intervention: Using methods we have established for an ongoing randomized clinical trial with 8 weeks of lentil supplementation, we will prepare 7 mid-day meals per participant per week to deliver a dose of 0 or 3 cups of lentils per week for the experimental and control groups. Meals are matched for macronutrient content (except for fiber), and ground turkey replaces lentils in the control meals. Participants will be instructed to consume food provided for their midday meal, and then to proactively reduce portion sizes and to not eat beyond fullness at the evening meal. This strategy exploits the satiety effect of pulses at the midday meal and the 'second meal effect' in which volitional consumption is reduced at the next meal, the evening meal.

A brief 4 pm online survey addressing satiety and a brief 8 PM online survey addressing gastrointestinal issues will be delivered once a week during the 12-week intervention to participants through personalized e-mails or texts. Each participant will be surveyed once weekly to determine whether they consumed the experimental meal that day, their perceptions of hunger, fullness, satiety, and satisfaction with that day's meal (at 4:00 pm), and their gastrointestinal comfort (level of bloating, flatulence, cramping, and comfort) throughout the day (at 8:00 pm). This methodology has been successfully implemented in our ongoing study to demonstrate that lentil meals are equally pleasing, produce greater satiety, and are well-tolerated.

Vist 3 and 4:

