Linear mixed effects models were used to assess the impact of a week and meal interaction on satiety measures. GI symptom severity was analyzed through a linear mixed effects model with symptom type and a week and meal interaction as predictors. Subject was the random effect for models assessing satiety and GI symptom severity.

Descriptive summary statistics were performed for participant physical and biological characteristics with general linear models used to determine if participants on average differed between meal groups before the intervention began. General linear models were used to assess

the impact of the dietary intervention on the following categories of variables: anthropometric measures (weight, fat mass percent, visceral adipose, and waist circumference); fasting blood lipid measures (CHOL, HDL, LDL, TG); fasting glycemic measures (GLU, INS, HOMA-IR); and fasting inflammation markers (GM-CSF, IFN- γ , TNF- α , IL-1 β , IL-6, IL-10, IL-17, IL-23). Fasting inflammation markers were normalized using r package bestNormalize [38] prior to statistical analysis. Dependent variables were calculated as the change in values from baseline (post-intervention – pre-intervention). Predictor variables were shared within each category of variables and are as follows: anthropometric measures –meal group; blood lipid measures –meal group, visceral adipose tissue; glycemic measures –meal group, visceral adipose tissue, change in BMI, HbA1c; inflammation measures –meal group, visceral adipose tissue. Predictor variables for glycemic measures were chosen based on previous findings by Zeevi and colleagues [39].

Analysis of postprandial metabolic (TG, GLU, INS) and inflammatory (GM-CSF, IFN- γ , TNF- α , IL-1 β , IL-6, IL-10, IL-17, and IL-23) measures were conducted by summarizing each makers measurements at timepoints 0 (fasting) and 1, 2, 3, 4, and 5 hours postprandially as net area under the curve (AUC) using the auctime [40] R package. Each dependent variable was then summarized as the change in AUC (post-intervention – pre-intervention). AUC values for inflammation markers were normalized using r package bestNormalize [38] prior to statistical analysis. General linear models were used to assess the impact of intervention meal group on each dependent variable. Predictor variables were identical to variables utilized in corresponding fasting models.

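### With subject as the only random effect, meal-by-week tests for satiety and GI symptoms may be miscalibrated, and the plan does not state week coding or covariance

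*Combined protocol and SAP*

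**What the plan says.** The Statistical Plan describes two models for the weekly surveys. For satiety: "Linear mixed effects models were used to assess the impact of a week and meal interaction on satiety measures". For tolerability: "GI symptom severity was analyzed through a linear mixed effects model with symptom type and a week and meal interaction as predictors". One sentence gives the random part of both: "Subject was the random effect for models assessing satiety and GI symptom severity".

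The data structure is in the Dietary intervention section of the Study Protocol. The 4 pm satiety survey and the 8 pm GI survey "will be delivered once a week during the 12-week intervention to participants through personalized e-mails or texts". The evening survey records "their gastrointestinal comfort (level of bloating, flatulence, cramping, and comfort) throughout the day".

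The plan does not say whether week is a number or a factor. For these models it gives no residual correlation structure, robust standard error, significance level or sample size.

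**The concern.** A subject intercept alone implies that any two of a person's reports, given the fixed effects, have the same correlation. Weeks 1 and 2 are then no more alike than weeks 1 and 12, and two symptoms from one evening are no more alike than two symptoms reported months apart.

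The term of interest is meal by week, and meal is assigned to people. With linear week, the test compares average slopes between two groups of people, so its error should include person-to-person variation in slope. The named model has no term for that. In the GI model, items that share one evening's disturbance would also be counted as separate evidence.

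At stake are statements on how satiety or tolerance develops over the 12 weeks in the two arms. If the standard error is too small, a difference in trend may be reported where there is none. If it is too large, a real one may be missed.

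**Working it through.** The plan states no figure to reproduce.

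**Inputs from the documents.** 12 weekly surveys; four GI items per evening; symptom type as a predictor in a single GI model; subject as the named random effect. If all four items are modelled and every survey is answered, that is 12 × 4 = 48 GI rows per person.

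**Assumed inputs.** Two-sided 5% level, 20 per arm (35 per arm gave almost the same results), complete data, and the variance components shown below. All results are under no meal effect.

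**Satiety, linear week.** For weeks 1 to 12 the sum of squares about the mean is 143. Let the residual variance be 1 and the between-person slope SD be τ per week, in residual SD units.
- True variance of one person's slope: τ² + 1/143.
- Variance the intercept-only model uses: its pooled residual, 1 + (143/11)τ² = 1 + 13τ², divided by 143.
- Ratio, true to model: (1 + 143τ²)/(1 + 13τ²).
- τ = 0.05: 1.3575/1.0325 = 1.31. The model SE is 0.87 of the true SE, and type I error is 2[1 − Φ(1.96/√1.31)] = 8.7%.
- τ = 0.10: 2.43/1.13 = 2.15. The SE ratio is 0.68 and type I error is 18.1%.

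Simulation (4,000 trials per scenario) agrees for linear week and adds the factor-week test on 11 df:

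| Satiety scenario | Linear week | Week as factor |
|---|---|---|
| Equal within-subject correlation | 5.6% | 4.5% |
| Slope SD 0.05 | 8.9% | 4.8% |
| Slope SD 0.10 | 19.2% | 6.7% |
| AR(1) residual, ρ = 0.2 | 10.3% | 5.7% |
| AR(1) residual, ρ = 0.4 | 16.5% | 6.7% |
| AR(1) residual, ρ = 0.6 | 25.1% | 9.2% |

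**GI, four stacked items.** Let v be the shared evening (subject-by-week) variance, u the subject-by-symptom variance and e the residual variance. Once the subject mean is removed, a person has 47 df: evenings contribute 4 × 11 × v = 44v to the sum of squares, and symptoms contribute 12 × 3 × u = 36u.
- The pooled residual is e + (44v + 36u)/47.
- The true variance of the weekly mean of four items, on the same scale, is 4v + e.
- Ratio R = (4v + e)/[e + (44v + 36u)/47].
- Approximate type I error is 2[1 − Φ(1.96/√R)] for linear week and P(χ²₁₁ > 19.68/R) for factor week.

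| v, u, e | R | Linear week | Week as factor |
|---|---|---|---|
| 0.25, 0, 1 | 2/1.234 = 1.62 | 12.4% | 35% |
| 0.25, 0, 0.75 | 1.75/0.984 = 1.78 | 14.2% | 44% |
| 0.25, 0.5, 0.75 | 1.75/1.367 = 1.28 | 8.3% | 17% |
| 0, 0.5, 1 | 1/1.383 = 0.72 | 2.1% | 0.4% |

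Repeated simulations agree. The shared evening effect alone gives about 12% to 15% (linear) and 36% to 46% (factor). With subject-by-symptom variance of 0.5 added, the figures are about 8% to 9% and 17% to 18%. Subject-by-symptom variance alone gives about 2% to 3% and under 1%.

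**Check of the remedy.** Comparing subject-level slopes between arms, which in balanced data is equivalent to adding a subject week slope, gave 5.0% (satiety, AR(1) ρ = 0.4), 5.4% (satiety, slope SD 0.10) and 4.7% (GI, 0.25/0.5/0.75), all with linear week.

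**The case against.** The strongest reply is that nothing in the documents shows the assumed components to exist. If all of a person's reports really are equally correlated, the named model is correct and there is no inflation. That people adapt to lentils at different rates is plausible, but the documents do not say so. This stands, and it limits the point to a risk of stated size.

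For GI, even the direction is open. Leaving out subject-by-symptom variation enlarges the pooled residual and can more than offset the evening effect. A reader might infer that stacking symptoms always makes intervals too narrow; the last row of the GI table shows the reverse. A reader might also infer that coding week as a factor is the safer choice. That holds for satiety in these scenarios, but with a shared evening effect it is much worse for GI.

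The description may also be abbreviated. Naming subject as the random effect does not strictly exclude a random slope, and the plan does not say outright that the comfort item is among the modelled symptom types. If a slope or residual structure was used, the plan should state it.

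Last, these are satiety and tolerability outcomes. Objective 1, on postprandial triglycerides and inflammation, is analysed with change-in-AUC general linear models, which this does not touch.

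**Conclusion.** The point holds as a risk of miscalibration in the meal-by-week tests. It does not show that the standard errors are too small. Under the assumptions above, type I error for satiety is about 9% to 19% with linear week and slope SD of 0.05 to 0.10, and about 5% to 7% with factor week. For GI it runs from under 1% to about 46%, depending on which omitted component dominates and how week is coded.

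A reader might infer that a finding of greater average satiety with lentils is also compromised. The documents do not support that: in balanced data the subject intercept gives the right error for the week-averaged meal difference, which stayed at 4.5% to 5.5% in the scenarios simulated. Exposed are claims about change over weeks and meal differences read at a particular week. The latter include the meal coefficient in a model with uncentred linear week, since it refers to week 0. The triglyceride and inflammation results are unaffected.

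**What to change.** State whether week is linear or a factor, and give the covariance structure of each model.
- **Satiety:** random intercept and random week slope per subject, or a serially correlated residual.
- **GI:** random intercept and week slope per subject, plus random intercepts for subject-by-week and subject-by-symptom. State which survey items count as symptom types.
- **If a model does not converge:** keep the fixed effects and use cluster-robust standard errors by subject with a small-sample correction.

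This takes about one line of model code per outcome and no new data. The plan describes these analyses in the past tense, so it may mean refitting the models. The cost is wider intervals in some cases and occasional handling of non-convergence.

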The first 20-30 minutes of the initial laboratory visit is devoted to walking the participant through the procedures and risks of the study, as well as answering any questions they might have prior to signing the informed consent document. Participants will then be asked to complete a series of questionnaires including: a 1-page health screening (AHA/ACSM Health/Fitness Facility Preparticipation Screening Questionnaire), 1-page Physical Activity Questionnaire, and a 1-page Demographic Questionnaire (Race and Ethnicity Questionnaire). The participant will also complete a body composition analysis as described below.

Measurement of muscle and fat tissue using bioelectrical impedance analysis: This test simply involves standing on a scale with your feet and hands on sensors for a few seconds. A very low electrical current that you cannot feel and that is not dangerous is transmitted and received across the sensors. The technology is commonly used in a variety of settings such as gyms and health screenings, but the instrument that we will use is more sophisticated in being able to estimate muscle and fat tissue in different regions of your body, including the abdominal cavity that is particularly important for predicting risk of diabetes.

Visit 2:

During Visit 1, our team will work with participants to determine an appropriate meal (breakfast or lunch) to eat that contains approximately 50 g of fat and to schedule a visit (Visit 2) approximately 3-4 hours after consuming this meal. Participants will come to the lab and have blood drawn according to standard procedures, where briefly blood is collected via venous puncture from a forearm vein.

Random Assignment: Participants will be randomized into Pulse or Control groups after Visit 2 if their non-fasting serum TG concentration 3-4 hours after a meal of the participant's choosing is greater than 175 mg/dl. Individuals with non-fasting TG levels less than 175 mg/dl will not complete the 12 week dietary intervention and will receive the benefits that were a part of their conducted visits in addition to monetary payments, prorated to the their total time spent in the study.

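### Fasting TG, insulin and HOMA-IR are analysed as untransformed change with no adjustment for their baseline value, which may cost precision if their variation grows with level

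*Combined protocol and SAP*

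**What the plan says.** All of this is in the Statistical Plan. The fasting metabolic outcomes are "fasting blood lipid measures (CHOL, HDL, LDL, TG); fasting glycemic measures (GLU, INS, HOMA-IR", analysed by general linear models. The outcome in each model is a plain difference: "Dependent variables were calculated as the change in values from baseline (post-intervention – pre-intervention".

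A transformation is stated for one group of fasting outcomes only: "Fasting inflammation markers were normalized using r package bestNormalize [38] prior to statistical analysis". The postprandial section repeats the pattern. Inflammation AUCs are normalised ("AUC values for inflammation markers were normalized using r package bestNormalize [38] prior to statistical analysis"), and nothing is stated for the TG, GLU and INS AUCs, which also enter as differences ("Each dependent variable was then summarized as the change in AUC (post-intervention – pre-intervention").

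The predictors are "blood lipid measures –meal group, visceral adipose tissue; glycemic measures –meal group, visceral adipose tissue, change in BMI, HbA1c". The pre-intervention value of the outcome is not among them. For TG, INS and HOMA-IR the plan states no residual check, robust method or outlier rule, and it gives no reason for treating them differently from the cytokines.

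**The concern.** TG, insulin and HOMA-IR are strictly positive, and HOMA-IR is a product of glucose and insulin, so proportional error in either carries through to it. For such measures it is a reasonable working assumption that a person's visit-to-visit variation scales with their level. If it does, a participant at four times another's level has four times the SD of change and 4² = 16 times the variance. The raw difference then gives high-level participants a large share of the residual variance, and the estimate leans on them.

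Separately, a change score fixes the slope of post on pre at 1. With imperfect pre-post correlation the true slope is usually below 1, and estimating it recovers precision on either scale.

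What is at stake is precision and stability of the estimate for three fasting outcomes. Type I error is not at stake.

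**Working it through.** **Inputs.** The documents give no sample size, alpha, power, SD, distribution or pre-post correlation for any outcome, so there is no planned figure to reproduce. Everything below is assumed: 1:1 arms of 20-30, two-sided alpha 0.05, SD of log level σ = 0.3, 0.5 or 0.7, pre-post log correlation ρ = 0.7, no dropout, no other covariates. A log transform stands for a normalising one.

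**Effect size.** Under proportional variation the effect was set so that a t test on log change has nominal 80% power: δ = σ√(2(1−ρ)) × √(2/n) × (1.960 + 0.842). Examples:
- n = 30, σ = 0.3: 0.3 × 0.775 × 0.258 × 2.802 = 0.168, a reduction of 1 − e^(−0.168) = 15%.
- n = 20, σ = 0.7: 0.7 × 0.775 × 0.316 × 2.802 = 0.480, a reduction of 38%.

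These are devices for comparing methods, not effects that the documents predict. Under constant variation the effect was additive and set to give raw change nominal 80% power.

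**Analytic check of baseline adjustment on the log scale.** The SD of log change is σ√(2(1−ρ)); the residual SD after adjustment is σ√(1−ρ²). Their ratio is √(2/(1+ρ)) = √(2/1.7) = 1.085. Large-sample power is therefore Φ(2.802 × 1.085 − 1.960) = Φ(1.08) = 86%, against 80% for log change.

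**Simulated power.**

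| Assumed visit-to-visit variation | Raw change (as planned) | Raw post adjusted for raw pre | Log post adjusted for log pre |
|---|---|---|---|
| Proportional to level | 51-73% | 69-84% | 83-86% |
| Constant on raw scale | 76-78% | 77-81% | 66-79% |

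In the first row the loss for raw change grows with σ: at 20-40 per arm and ρ = 0.6-0.8, raw change has 69-73%, 60-65% and 50-55% power at σ = 0.3, 0.5 and 0.7, against 78-80% for log change. A good part of the gain comes from baseline adjustment alone.

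In the second row raw-scale adjustment gains little, because pre and post are then already closely correlated. The size of the reversal depends on the assumed spread. In runs with levels around 150 and a constant SD of 15, unadjusted log change had 57-76% against 78-79% for raw change.

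**Weight of few participants.** Under proportional variation, the tenth of participants with the largest squared deviations carry 47-49%, 55-58% and 63-67% of the raw-change sum of squares at σ = 0.3, 0.5 and 0.7. On the log scale that share is 42-43%, so the excess is modest at σ = 0.3 and marked at 0.7.

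**Validity.** With no effect, the raw-change test rejected in 4.1-5.4% of simulated trials.

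**Entry rule.** Selecting participants with high screening values (30 per arm) gave raw change 72%, 65% and 56% against 80% for log change. Without selection raw change had 71-73%, 63-64% and 53%. Selection neither removes the loss nor worsens it.

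**The case against.** The strongest objection is that the consequence rests on an assumption that the documents neither state nor allow to be checked. Skewed levels do not by themselves make change scores heavy-tailed; variation must also grow with level. If it is constant on the raw scale, the planned analysis is fine and a log analysis can lose power. This stands, and it is why the point is conditional.

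A reader might infer several stronger things that the documents do not support:
- *That a few participants do dominate and power is lost.* No SD or distribution is given, so this can only be said to be possible.
- *That the TG entry rule makes extreme values likely.* The requirement that TG "is greater than 175 mg/dl" (Random Assignment) concerns a non-fasting sample 3-4 hours after a meal. It is not fasting TG and says nothing direct about INS or HOMA-IR. No upper limit is stated there, but eligibility is confirmed by phone interview and those criteria are not set out in this document. A lower cutoff also trims the low tail.
- *That the trial's key outcomes are affected.* The first objective is postprandial TG and inflammation. The fasting measures discussed here are not named in any objective.
- *That an additive treatment effect would rescue the raw analysis.* With an additive effect and proportional variation, raw change had 43-71% power and log change 80-99%. The structure of the variation decides the matter, more than the scale of the effect.

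Two further objections stand in part. The comparison omits the planned covariates, some of which may absorb part of the baseline signal, so the real gain may be smaller. And the plan is written in the past tense, so a change of scale now may be a choice made after the results are known.

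**Conclusion.** The point holds as a minor, conditional one. It is a fact of the text that fasting TG, INS and HOMA-IR are analysed as untransformed change without their baseline value, while inflammation markers are normalised and no reason is given. The planned test is valid, and nothing here suggests a biased or false result.

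Whether precision is lost depends on how visit-to-visit variation relates to level. With proportional variation and the assumed inputs, the shortfall is about 10 points at its smallest (83 − 73) and about 35 at its largest (86 − 51). With constant variation there is no shortfall, and the log model ranges from about level to roughly 10 points worse, or more under other assumed spreads. Adjusting for baseline is the more secure half of the recommendation, since it does not depend on which case applies. The log scale is a reasonable default for these three measures, with a limited downside.

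**What to change.** For fasting TG, INS and HOMA-IR, model log(post) with log(pre), the planned covariates and meal group as the effect of interest. Report the ratio of geometric means with its 95% CI. As a sensitivity analysis, give the raw-scale model adjusted for the raw baseline value, which covers the case of constant variation. State in one line why each group of outcomes is analysed on its scale. Leave the net AUCs on their current scale: they can be zero or negative, so a log is not generally available.

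The cost is SAP wording and a refit on measurements that the protocol already collects. Effects would read as percent differences and not in mg/dl or raw units, and some power is lost if variation is in fact constant on the raw scale. If the analyses have already been run, the planned change-score results should stay in the report and the new models be labelled post hoc.

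### Thirty outcomes are analysed as change scores without the outcome's own pre-intervention value as a covariate, which loses precision wherever the pre-post slope is clearly different from 1

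*Combined protocol and SAP*

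**What the plan says.** All the relevant text is in the Statistical Plan section of the combined protocol and SAP.

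**Outcomes.** Nineteen are measured at rest: 4 anthropometric, 4 fasting lipid, 3 fasting glycemic and 8 fasting inflammation markers. For these, "Dependent variables were calculated as the change in values from baseline", as post minus pre. Eleven are postprandial net AUCs (TG, glucose, insulin and the same 8 inflammation markers). For these, "Each dependent variable was then summarized as the change in AUC", again post minus pre.

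**Predictors.** The lists are given in full by category: "Predictor variables were shared within each category of variables and are as follows".
- Anthropometric: meal group only.
- Lipids and inflammation: meal group and visceral adipose tissue.
- Glycemic: meal group plus "visceral adipose tissue, change in BMI, HbA1c".
- Postprandial: "Predictor variables were identical to variables utilized in corresponding fasting models".

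**Baseline comparison.** The plan also has "general linear models used to determine if participants on average differed between meal groups before the intervention began".

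**Normalization.** The fasting inflammation markers are transformed, and likewise "AUC values for inflammation markers were normalized using r package bestNormalize". The text does not make clear whether this happens before or after the difference is taken.

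The diet, satiety and gastrointestinal outcomes use mixed models and are outside this point.

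**The concern.** A change score with no baseline term is a regression of the post value on the pre value with the slope held at 1. The true slope is the pre-post correlation times SDpost/SDpre. With equal SDs it equals the correlation, so visit-to-visit noise alone puts it below 1. The plan imposes a slope of 1 on body weight, fasting insulin, eight cytokines and 5-hour AUCs alike, and gives no reason to expect it for all of them.

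Two things follow when the slope is clearly different from 1. The group contrast is less precise than it need be. And a chance difference between the groups at baseline shifts the contrast by (1 − slope) times that difference. The plan tests for baseline differences, but its outcome models do not use the outcome's own baseline. The affected outcomes include the TG and inflammation AUCs, which serve the first specific objective.

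**Working it through.** **Count.** 4 + 4 + 3 + 8 = 19 anthropometric and fasting outcomes. 3 + 8 = 11 AUC outcomes. Total 30. By predictor set:
- 4 models with meal group only.
- 21 models that add visceral adipose tissue (4 fasting lipids, TG AUC, 8 fasting and 8 AUC inflammation markers).
- 5 glycemic models that add three covariates (fasting glucose, insulin and HOMA-IR; glucose and insulin AUC).

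None of the 30 contains the outcome's own pre-intervention value, and no other section adds it.

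**Inputs.** The document states no sample size, SD or pre-post correlation, so there is no figure of its own to reproduce. Assumed: n = 15 to 40 per arm with equal arms; r = SDpost/SDpre = 0.8 to 1.2; ρ = 0.3 to 0.9, taken after the predictors already in the model. Set SDpre = 1, slope b = ρr, and k = the number of other covariates.

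**Variance.** Per participant, the change score has variance 1 + r² − 2ρr and the baseline-adjusted residual has r²(1 − ρ²). These are linked by

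1 + r² − 2ρr = r²(1 − ρ²) + (1 − b)².

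The excess is therefore (1 − b)², which is zero only at slope 1. Allowing for the estimated extra term, the ratio of adjusted to change-score variance of the group contrast is

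ratio = [r²(1 − ρ²) / (1 + r² − 2ρr)] × [1 + 1/(2n − 4 − k)].

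Example with n = 15, r = 1, ρ = 0.5, k = 0: (0.75/1.00) × (1 + 1/26) = 0.78.

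| r | n per arm | ρ = 0.3 | 0.5 | 0.7 | 0.9 |
|---|---|---|---|---|---|
| 0.8 | 15 | 0.52 | 0.59 | 0.65 | 0.63 |
| 0.8 | 40 | 0.51 | 0.58 | 0.64 | 0.62 |
| 1.0 | 15 | 0.68 | 0.78 | 0.88 | 0.99 |
| 1.0 | 40 | 0.66 | 0.76 | 0.86 | 0.96 |
| 1.2 | 15 | 0.79 | 0.90 | 1.00 | 1.01 |
| 1.2 | 40 | 0.77 | 0.88 | 0.98 | 0.99 |

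**Where adjustment loses.** It loses only if (1 − b)² < r²(1 − ρ²)/(2n − 4 − k), and never by more than 1/(2n − 4 − k).
- At 15 per arm the bound is 1/26 = 3.8% (k = 0), 1/25 = 4.0% (k = 1) or 1/23 = 4.3% (k = 3). At 40 per arm it is 1.3 to 1.4%.
- At 15 per arm (k = 0) the losing range is ρ above 0.926 for r = 1.0, 0.79 to 0.96 for r = 1.1, and 0.69 to 0.91 for r = 1.2.
- At 40 per arm it is ρ above 0.974, 0.85 to 0.95, and 0.76 to 0.89.
- There is no losing range at r = 0.8 or 0.9.

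**Power.** Take a contrast with 80% power on the change score at 15 per arm. A noncentral t calculation averaged over random baseline imbalance gives, for ρ = 0.3, 0.5, 0.7, 0.9: 93, 89, 85, 80% (r = 1.0); 97, 95, 93, 94% (r = 0.8); 88, 84, 80, 79% (r = 1.2).

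**Chance imbalance.** At 15 per arm the baseline difference between groups has SD √(2/15) = 0.37 pre-SD. An imbalance of that size moves the change-score contrast by |1 − b| × 0.37. In pre-SD units, over the same ρ values: 0.26, 0.18, 0.11, 0.04 (r = 1.0); 0.28, 0.22, 0.16, 0.10 (r = 0.8); 0.23, 0.15, 0.06, 0.03 (r = 1.2).

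**Simulation check.** There were 40,000 trials per cell under no effect, without and with one baseline covariate standing in for visceral adipose tissue. Variance ratios agreed with the formula to within 0.01, the mean change-score contrast was within 0.003 of zero, and type I error was 4.8 to 5.2%. Models containing change in BMI were not simulated.

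**The case against.** The strongest reply is that the change score is a valid estimator in a randomized comparison. The simulation shows no bias and correct type I error, so the plan contains no error, only a less efficient choice. That stands, with limits. It holds on average for the 4 anthropometric models. For the 21 models with visceral adipose tissue it holds only if that covariate is the baseline measurement, and the plan does not say which visit it comes from. It is not claimed for the 5 glycemic models, which condition on change in BMI, a post-randomization variable. That is a separate issue, and a baseline term does not repair it.

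Second, every magnitude is assumed, and the plausible results run from about half the variance to a small loss. This also stands: the document does not show which outcomes gain, and stable ones such as weight may gain nothing. But the potential saving is large and the worst cost is about 4%, so not knowing the slopes favours adjusting.

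Third, the figures apply cleanly to fewer than 30 outcomes. Setting aside the 5 glycemic outcomes and the 16 inflammation outcomes, whose normalization order is unclear, leaves 9: the anthropometric measures, the fasting lipids and TG AUC, the last five still conditional on baseline visceral adipose tissue. That limits the numbers. The baseline term is missing from all 30 models all the same.

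Fourth, visceral adipose tissue and HbA1c may already carry some baseline information. They may, which is why ρ is taken after existing predictors, but they do not replace the outcome's own value.

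**Conclusion.** The concern holds. The omission is certain for all 30 outcomes. Its cost is efficiency: nil or slightly negative where the slope is near 1, and substantial where it is not. If the SDs are equal, the correlation is 0.5 and there are 15 per arm, the change score gives up roughly 9 points of power (80% against 89%). If the correlation is 0.9 it gives up essentially nothing. For the 16 inflammation outcomes these figures apply only if values are normalized before the difference is taken. This should be corrected, but it does not invalidate the planned comparison.

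**What to change.** - Add the pre-intervention value of the same outcome as a covariate in all 30 models; for AUC outcomes use the pre-intervention AUC. The change can stay as the response, since with the baseline term included the group coefficient is the same as when the post value is modelled.
- Apply this as one rule to every outcome, not as a choice made by outcome after seeing the data.
- For the 16 inflammation outcomes, fit one bestNormalize transformation per outcome to both visits together and apply it before taking the difference, so that covariate and response share a scale. This is secondary to the baseline term itself.
- State that the visceral adipose tissue covariate is the baseline measurement.
- If the analyses have been run, report the adjusted results beside the originals and label them post hoc.

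The cost is one degree of freedom per model, a changed normalization step for 16 outcomes, and no new data. Where the slope is near 1, it is up to about 4% of variance at 15 per arm. If the change itself was normalized originally, the 16 refits will be on a different scale and their estimates will not be directly comparable with the originals. The plan is in the past tense and dated 10/22/2024, so the likely work is 30 refits reported as a labelled sensitivity analysis.
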